### 9.4.3. Safety Analyses

All safety analyses will be based on the Safety Analysis Set as defined in [Section 9.3.3](#).

TEAEs are AEs that start on or after the date and time of the first administration of study treatment. TEAEs occurring until the Follow-up Visit (or the End of Treatment Visit for

subjects continuing into the post-study access program or another prophylactic treatment) will be summarized. All AEs regardless of when they were reported will be listed.

AEs will be coded using the Medical Dictionary for Regulatory Activities (MedDRA). There will be periodic updates of the MedDRA version. The latest licensed version will be used, and version updates will be implemented upon availability. AEs will be primarily classified by MedDRA PT. Analyses will be performed by system organ class (SOC) and PT. Aggregated incidences at SOC level and any TEAE will also be provided.

Coronavirus disease 2019 (COVID-19)-associated AEs will be included in TEAE tables identified by standard MedDRA coding.

Subjects with multiple occurrences of the same TEAE will be counted once in the total of those experiencing this PT. Similarly, a subject with 1 or more PT in a SOC will be counted once in the total of those experiencing PTs in that SOC. Percentages for subject incidence rates will be based on the Safety Analysis Set.

Analyses of other safety assessments (ie, vital signs, clinical laboratory safety markers, etc) will be described in the SAP.

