### **10.2. Adverse Events and Serious Adverse Events: Definitions and Procedures for Recording, Evaluating, Follow-up, and Reporting**

#### **10.2.1. Definitions**

##### **10.2.1.1. Adverse Event**

An AE is any untoward medical occurrence in a clinical study subject administered an investigational product and that does not necessarily have a causal relationship with this treatment. An AE can, therefore, be any unfavorable and unintended sign (including an abnormal, clinically significant laboratory finding), symptom, or disease temporally associated with the use of a medicinal (investigational) product, whether or not considered related to the medicinal (investigational) product.

The observation period for AEs is defined in [Section 10.2.4](#).

AEs may include the following:

- Exacerbation (ie, an increase in the frequency or severity) of a preexisting condition. Preexisting conditions should be recorded on the Medical History CRF and only reported as an AE if there is an increase in the frequency or severity of the condition during the study.
- A clinical event occurring after consent and before investigational product administration.
- Intercurrent illnesses with an onset after administration of investigational product.

AEs do not include the following:

- Events identified at [Screening](#) that meet exclusion criteria
- Medical or surgical procedures (the condition that leads to the procedure is the AE)
- Situations where an untoward medical occurrence has not taken place. For example:
  - Planned hospitalizations related to preexisting conditions that have not worsened
  - Hospitalizations that occur for procedures not due to an AE (eg, cosmetic surgery)
  - Hospitalizations for a diagnostic procedure where the hospital stay is less than 24 hours in duration or for normal management procedures (eg, chemotherapy)
- Overdose of investigational product or any concomitant therapy that does not result in any adverse signs or symptoms

For laboratory and other safety parameters (eg, vital signs), any instances of absolute values or changes at any visit after study start that are considered by the investigator as clinically

significant must be recorded on the AE CRF. In addition, at the investigator's discretion, any changes or trends over time in laboratory parameters may be recorded on the AE CRF if such changes or trends are considered to be clinically relevant, even if the absolute values are within the reference range.

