Laboratory findings do not need to be reported as AEs in the following cases:

- Laboratory parameters already beyond the reference range at Screening, unless a further increase / decrease can be considered an exacerbation of a preexisting condition.
- Abnormal laboratory parameters caused by mechanical or physical influences on the blood sample (eg, in vitro hemolysis) and flagged as such by the laboratory in the laboratory report.
- Abnormal parameters that are obviously biologically implausible (eg, values that are incompatible with life or outside the measuring range).
- An abnormal laboratory value that cannot be confirmed after repeat analysis, preferably in the same laboratory (ie, the previous result could be marked as not valid and should not necessarily be reported as an AE).

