#### **10.2.4. Observation Period for Adverse Events**

The observation period for the reporting of AEs (and SAEs) for an individual subject will start at the time of giving written informed consent for participation in the current study and finish upon the subject's final visit.

If the investigator becomes aware of an SAE that has started after the observation period has ended, and there is at least a possible causal relationship with the investigational product or medical device constituent, the event must be reported to the sponsor following the same timelines and procedures described for SAEs occurring during the study (Section 10.2.6.2).

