10.2 Adverse Events

AEs will be coded using the MedDRA dictionary. There will be periodic updates of the MedDRA version. The latest licensed version will be used, and version updates will be implemented upon availability. AEs will be primarily classified by MedDRA PT. Analyses will be performed by SOC and PT. Aggregated incidences at SOC level and any TEAE will also be provided.

TEAEs are AEs that start on or after the date (and time if available) of the first administration of IP until the Follow-up Visit. TEAEs until the Follow-up Visit will be summarized. Subjects who continue with CSL312 or another prophylactic treatment after this study will not enter into the Follow-up Period and thus only TEAEs until the EoT are reported.

For the primary estimand, the TEAEs will be summarized until the EoT Visit (see [Section 10.2.1](#)).

All AEs regardless of whether they were treatment-emergent or not will be listed.

COVID-19-associated AEs will be included in TEAE tables identified by standard MedDRA coding.

Subjects with multiple occurrences of the same TEAE will be counted once in the total of those experiencing this PT. Similarly, a subject with 1 or more PT in a SOC will be counted once in the total of those experiencing PTs in that SOC. Percentages for subject incidence rates will be based on the Safety Analysis Set.

Injection site reactions (ISRs) will be summarized by an additional (artificial) "SOC" called "Injection Site Reactions". To identify PTs belonging to this (artificial) "SOC" of ISRs, CSL will be provided a list in Excel format of all PTs found in the database with verbatim. CSL will review this list and mark the corresponding PTs in a column of this Excel sheet. These identified PTs will be reported in the (artificial) "SOC" of ISR as well as in their original MedDRA SOC. For the overall "Any TEAE" entry at the beginning of the table, these ISRs will be reported once. ISRs will be presented as first "SOC" following the overall "Any TEAE" entry. The MedDRA SOC and PTs will be presented in descending frequency of the overall category. Within the same frequency, SOC and PTs will be ordered alphabetically.

Where AE start dates and/or times are missing or partially missing, AEs will be assumed to be treatment-emergent, except if the partial start dates and/or times or the AE end date and/or time indicate that the AE started before the first administration of IP (see [Table 5](#)).

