Table 5 TEAE Assignment in Case of Missing AE Start Date Elements

Missing elements of AE start	Rule	
Regardless of any missing information for AE start: AE end date / time < IP start date / time		non-TEAE
Otherwise (i.e., if AE end date / time \geq IP start date / time)		
- All		TEAE
- Day and Month	AE start year \geq IP start year	TEAE
	AE start year < IP start year	non-TEAE
- Day	AE start month / year \geq IP start month / year	TEAE
	AE start month / year < IP start month / year	non-TEAE
- Time	AE start date \geq IP start date	TEAE
	AE start date < IP start date	non-TEAE

If AE start dates or end dates are missing or partially missing for an AE, no duration will be calculated. If for a TEAE the relationship to study treatment is missing the worst case will be assumed for summarizing analysis (i.e., the relationship to study treatment will be assumed to be "Related"). In case of missing study treatment relationship for non-treatment-emergent AEs, the relationship will be set to "Not related".

Temporally associated TEAEs are defined as AEs with an onset between the start of the injection and up to 24 hours after the end of the injection. In the case the time of the onset of the AE is missing, the AE is considered temporally associated, if the onset of the AE is between the day of the start of injection and the day of the end of injection + 1 day (inclusive). If the start date of the AE is (partially) missing the temporally association cannot be assessed.

Severe hypersensitivity including anaphylaxis is defined as AESI per study protocol . In addition to AESIs reported by Investigators per study protocol, events suggestive of any hypersensitivity including anaphylaxis will be identified for further review by:

- Standardised MedDRA Query "Hypersensitivity (SMQ)" (broad).
- Anaphylactic reaction (SMQ) (broad).
- Anaphylactic/anaphylactoid shock conditions (SMQ) (broad).

The broad scope includes narrow and broad search. The SMQ search does not account for severity (also non-severe cases will be included) while the AESI assessment by the investigator will do.

TEAE rates per subject year of exposure will be calculated as:

$$\text{TEAE rate per subject year} = \frac{\text{Number of TEAEs}}{\text{Subject Years of Exposure}}$$

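### The TEAE definition has no worsening clause, so an AE that starts between consent and first dose and worsens on CSL312 stays outside the primary safety endpoint unless the site opens a new record

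*Protocol*

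**What the plan says.** **Definition.** Protocol 9.4.3: "TEAEs are AEs that start on or after the date and time of the first administration of study treatment". SAP 10.2: "TEAEs are AEs that start on or after the date (and time if available) of the first administration of IP until the Follow-up Visit". Both look at onset only. SAP Table 5, which handles missing elements of the start date, follows the same logic: in its missing-time row, "AE start date < IP start date" gives a non-TEAE.

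**Collection.** Under Protocol 10.2.4 the AE observation period "will start at the time of giving written informed consent for participation in the current study". Protocol 10.2.1.1 includes among AEs: "A clinical event occurring after consent and before investigational product administration". Pre-dose AE records will therefore exist.

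**Worsening.** Protocol 10.2.1.1 deals with worsening in two places. The first covers conditions already present at entry: "Preexisting conditions should be recorded on the Medical History CRF and only reported as an AE if there is an increase in the frequency". A rise in severity qualifies too. The second is in the list of laboratory findings that need not be reported: "Laboratory parameters already beyond the reference range at Screening, unless a further increase / decrease can be considered an exacerbation of a preexisting condition". Protocol 10.2.5 and 10.2.6.1 ask sites to follow an AE until it resolves or stabilizes. They say nothing about a new record if it gets worse.

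**Use.** TEAEs are the variable of the primary safety estimand, summarized as a rate per subject year (Protocol 9.4.3.1, SAP 10.2.1). The AE tables in SAP 10.2.2 and 10.2.3, including those for serious, severe and related events, are restricted to TEAEs.

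**Missing causality.** A TEAE with no recorded relationship is summarized as related. For the rest, SAP 10.2 says: "In case of missing study treatment relationship for non-treatment-emergent AEs, the relationship will be set to" not related.

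**The concern.** A safety definition should pick up harm that arises or gets worse on treatment. Here, an AE with a known start before first dose is classified by that date whatever happens later. A child with mild abdominal pain five days before first dose, whose pain becomes severe and leads to admission a month into treatment, has one AE record with a pre-dose start. On the stated rule it is not a TEAE.

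The plan already accepts that worsening can be an adverse event, since it says so for pre-existing conditions and for abnormal Screening laboratory values. A complaint that began the day before consent and worsened on drug would be reportable and could become a TEAE. The same complaint beginning the day after consent would be an AE already, with no instruction that leads to a TEAE. Nothing in either document explains this difference.

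The stake is the numerator of the primary safety measure and of the TEAE tables that depend on it. Protocol Table 2 also lists SAEs among the secondary endpoints, to be summarized as events on treatment. SAP 10.2.3 tabulates serious TEAEs only, so an AE that becomes serious on drug after a pre-dose start would be listed but not counted. The study has no control arm in which the same omission would occur.

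**Working it through.** The plan gives no figure to reproduce: there is no hypothesis test, no sample size formula and no expected AE rate. The check therefore has three parts.

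**1. Apply the rules to four cases, each worsening on drug.**

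| Case | Governing text | Result |
|---|---|---|
| Condition present before consent | Protocol 10.2.1.1, exacerbation | Reportable AE; can be a TEAE |
| Laboratory value abnormal at Screening | Protocol 10.2.1.1, laboratory exception | Reportable if an exacerbation; can be a TEAE |
| Clinically significant change in examination, laboratory or vital-sign findings | Protocol Table 6, 8.3.2 and 10.2.1.1 | Recorded as an AE; can be a TEAE |
| Symptomatic AE starting after consent and before first dose | Protocol 9.4.3, SAP 10.2 | Non-TEAE; no instruction to open a new record |

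Only the last case has no route into the TEAE count. With a complete start date 10 days before first dose and an end date after it, the rule gives non-TEAE at any later severity. A separate record starting after first dose would be a TEAE.

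**2. Effect of one omitted event.** Inputs: 20 subjects targeted and at least 15 completing (Protocol 1.1); End of Treatment on Day 361 (Protocol 1.3). Assumption: every subject contributes 361 days.

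- Subject years = n × 361 / 365.25.
- n = 20: 20 × 361 / 365.25 = 19.77. One event: 1 / 19.77 = 0.051 per subject year.
- n = 15: 15 × 361 / 365.25 = 14.82. One event: 1 / 14.82 = 0.067 per subject year.
- Incidence: 1 / 20 = 5.0 points, or 1 / 15 = 6.7 points. This is a maximum, reached only if that subject has no other event of the same class.

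Tables are also given by regimen, where denominators are smaller. The documents do not give the split. At an assumed 5 to 10 subjects in a regimen, one subject is 20 to 10 points.

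**3. Number of events at risk, on assumptions only.** The documents give the window (up to 30 days, or 60 with sponsor permission) but none of the rates below.

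- AEs starting in Screening, at an assumed 3 to 6 per subject-year in 20 subjects: 20 × 30 / 365.25 × 3 = 4.9, and × 6 = 9.9. If all 20 had 60 days: 9.9 to 19.7.
- Still ongoing at first dose, at an assumed 20% to 30%: 0.20 × 4.9 = 1.0 to 0.30 × 9.9 = 3.0 (30 days); 0.20 × 9.9 = 2.0 to 0.30 × 19.7 = 5.9 (60 days).
- Of these, worsening on drug, at an illustrative 10%: 0.1 to 0.3 (30 days) and 0.2 to 0.6 (60 days) for the whole study.

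Only the last line counts events that the definition would misplace. It moves in proportion to three unsourced fractions, so it shows scale and is not an estimate.

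**The case against.** The strongest reply has four parts.

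*The events are visible.* A reader might infer that such an AE disappears into the listing of non-treatment-emergent AEs. It does not. SAP 10.2.3 also plans listings of SAEs, fatal SAEs, AEs leading to withdrawal and AEs leading to permanent discontinuation, and none of these is restricted to TEAEs. In about 20 children, with no hypothesis test, a reviewer can read them. This stands, but a listing does not correct a rate or a percentage.

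*Much worsening would produce a new record anyway.* A reader might infer that the event can never be counted. That is too strong. The examination, laboratory and vital-sign rules are not tied to medical history, and the CRF Completion Guidelines, which are not among the documents, may ask for more. This stands for objective findings. It leaves symptomatic AEs to site practice.

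*Few AEs will be at risk.* Active infection or fever within 24 hours defers the first dose (Protocol 1.3.1 and 1.3.2, footnotes), exclusion criteria 6 and 7 remove significant abnormalities and illness, and Screening can last zero days (SAP Table 3, note). This also stands. It is why 1 to 3 or 2 to 6 ongoing records should not be read as hidden TEAEs: those that do not worsen are correctly non-TEAEs.

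*Table 5 and the causality default are side issues.* Table 5 governs missing start elements only, and its missing-day row treats onset in the month of first dose as treatment-emergent. The gap comes from the definition itself. For causality, Protocol 10.2.3 requires an assessment for every AE and treats a missing one as related until clarified, so the not-related default is a residual rule and would rarely matter.

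**Conclusion.** The gap is real and narrow. On the text of both documents, a symptomatic AE that starts between consent and first dose and then increases in severity or becomes serious on CSL312 is left out of the primary TEAE rate and the TEAE tables, unless the site happens to open a new post-dose record. Comparable worsening of a condition that predates consent is reportable and can be counted.

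The direction is fixed: the numerator can only fall, while exposure time does not depend on how the AE is classified. The size per event is about 0.05 to 0.07 per subject year overall, assuming 361 days for each of 20 or 15 subjects. For one serious event it is at most 5 percentage points of incidence at n=20.

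The documents do not support a claim that the primary rate will be materially biased. They give no AE rate, no proportion ongoing at first dose and no proportion worsening, and the entry rules make the expected number small. The case for acting rests on consistency and on the negligible cost of the correction.

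**What to change.** 1. In Protocol 9.4.3 and SAP 10.2, define a TEAE as an AE that starts on or after first IP, or that started before first IP and increases in severity or becomes serious on or after first IP.
2. Count each worsening once, by one stated mechanism. Either flag the pre-dose record as a TEAE from the date of worsening, or enter the worsening as a new AE dated at its onset and leave the pre-dose record as a non-TEAE. Using both would add two events to the rate for one worsening. If the flag is chosen, the date of worsening must be captured and used for the 3-month windows, because SAP 10.2.2 allocates TEAEs by start date.
3. Tell sites which mechanism applies. Protocol 10.2.1.1 makes an exacerbation reportable but gives no dating rule, so this has to be written out.
4. Align SAP Table 5 so that its non-TEAE rows do not override the new clause.
5. Apply the TEAE rule for missing relationship to these events.

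The cost is one clause in a new SAP version and in the protocol at its next amendment, a CRF-completion note and some data queries. The reported TEAE rate may rise slightly. No study procedure or treatment changes.

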#### **9.4.3.1. Primary Safety Estimand**

The primary safety interest is to assess whether TEAEs occurred at least once during SC administration of CSL312 in the prophylactic treatment of pediatric subjects with C1-INH HAE during treatment from the first investigational product administration at Day 1 Visit through the End of Treatment Visit or the latest available visit or event (whichever is later) for subjects without the End of Treatment Visit while subjects are allowed to treat HAE attacks with on-demand medications.

The primary safety estimand, in line with the primary safety interest of the study, follows the treatment policy strategy and is described as follows:

- Treatment condition: Q1M or Q2M treatment with 100 mg CSL312
- Population: The target patient population, defined by eligibility criteria and who received at least 1 dose of investigational product (Safety Analysis Set)
- Variable: TEAEs
- Intercurrent events: The occurrence of an intercurrent event is ignorable. All observed values will be used, regardless of occurrence of any of the following intercurrent events:
  - Administration of on-demand medication in addition to prophylactic treatment with CSL312
  - Prohibited concomitant medications due or not due to COVID-19 or COVID-19 vaccination
  - Treatment adherence or early treatment discontinuation due or not due to COVID-19
- Population-level summary: TEAE rate per subject year

#### 9.4.3.2. Analysis of Primary Safety Endpoint

Following the estimand described in [Section 9.4.3.1](#), the TEAEs for pediatric subjects with C1-INH HAE will be summarized by event rate per subject year using the Safety Analysis Set. All summary tables described will be by 100 mg Q2M, 100 mg Q1M, and overall.

TEAE rates per subject year will be calculated as follows:

$$\text{TEAE rate per subject year} = \frac{\text{Number of TEAE}}{\text{Subject years}}$$

where subject years will be the sum of the time in years that subjects were exposed to study treatment at that dosing regimen during the respective safety evaluation period. For the calculation of time exposed to a specific dosing regimen, each study day will be counted under the corresponding dosing regimen.

In addition, TEAEs will be summarized by the number of subjects and percentage of subjects experiencing at least 1 TEAE, the number of events, as well as the event rate per injection.

TEAE rates per injection will be calculated as follows:

$$\text{TEAE rate per injection} = \frac{\text{Number of TEAE}}{\text{Number of injections}}$$

where number of injections will be the sum of the injections that subjects received during the respective safety evaluation period at a specific dosing regimen the TEAE is assigned to.

An overview summary of TEAEs as well as a table by SOC and PT will be provided.

To evaluate the COVID-19 impact on the primary endpoint, the overview summary of TEAEs and the summary table by SOC and PT will be repeated as a sensitivity analysis excluding all of the COVID-19 related TEAEs (per the corresponding Standardized MedDRA Query).

All AEs will be presented in a by-subject listing.

#### 9.4.4. Pharmacokinetics Analyses

The PK parameters after SC administration of CSL312 at steady state are primary endpoints in this study. The PK analysis will be performed using the PK Analysis Set.

##### 9.4.4.1. Analysis of Primary Pharmacokinetic Endpoint

Plasma concentrations of CSL312 will be listed by individual subjects and will be summarized by nominal time points and by dosing regimen (ie, 100 mg Q2M, 100 mg Q1M) using the PK Analysis Set. Plasma concentrations will be summarized with descriptive statistics: n, mean, SD, percent coefficient of variation (CV%), median, minimum, maximum, first and third quartiles for continuous variables, and geometric mean and its respective 90% CI.

PK parameters will be derived using noncompartmental PK analyses and will be summarized descriptively by dosing regimen (ie, 100 mg Q2M, 100 mg Q1M). PK parameters will include maximum plasma concentration ( $C_{\max}$ ), trough plasma concentration ( $C_{\text{trough}}$ ), and time to reach maximum plasma concentration ( $T_{\max}$ ). The following descriptive statistics will be presented for all PK parameters, except for  $T_{\max}$ : n, mean, SD, CV%, median, geometric

mean, geometric CV%, minimum, and maximum. For  $T_{max}$ , n, median, minimum, and maximum will be provided.

Additional information on the analyses of PK parameters will be provided in the SAP.

